## **11. Investigator's Qualifications**

The PI, [name], has conducted a number of experiments similar to this one with amputees. The Co-PI, [name], is a certified prosthetist specifically trained to work with individuals with amputation and fit prosthetic devices to them. Three of the prosthetic knees used in this protocol are clinically available through manufacturers and used broadly in the prosthetics clinical community. These are the devices that will be brought home for 1 week testing protocols with participants. The fourth device is our own experimental investigational device and the testing of this device was IRB approved previously at Georgia Tech with a separate, but related protocol. All members listed on this IRB protocol have CITI training.

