**Specific Aims:** Aim 1 will assess functional performance associated with use and wear of three different commercially available MPKs and one research grade powered knee in 17 individuals with TFA. Aim 2 will assess subjective patient reported preferences associated with use of the same four prosthetic knees along with collection of subject specific anthropomorphic characteristics that may correlate with MPK choice. Aim 3 will generate the clinical decision algorithm for MPK selection.

**Study Design:** Our study revolves around clinical tests and outcomes measures to evaluate the biomechanical performance and patient reported outcomes of three different commercially available MPKs and a single research grade powered knee in individuals with a TFA. We will test the hypothesis that differences will emerge between individuals when wearing the different knees and that these differences will be predictable. Subjects will ambulate over various terrains to simulate community ambulation with each MPK (Aim 1) allowing for assessment of the functional performance of each MPK. Through collection of individual anthropomorphic data and psychometric outcomes measures (Aim 2), we predict individual preferences and biomechanical improvements will emerge between the various MPKs

allowing for the generation of a clinical decision algorithm for MPKs (Aim 3).

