4. Acclimation time varies widely in the literature (from 3-10 hours [2, 3] to months [4]) and is acknowledged to have important implications for this study's results. In this study, subjects will go through an initial tuning and training process similar to what is done in clinic scenarios including tuning knee parameters and training over the various terrains in the lab including stairs, ramps and a treadmill. Subjects will then proceed to wear the prosthesis for 1 week at home and in the community in order to acclimate to the device and then return to the lab for testing. A sensor to collect data about the number of steps participants take will be attached to the prosthesis and/or your shoes. This sensor does not have a GPS and will not record where subjects go. Subjects will use their same socket, prosthetic foot and shoe during each knee evaluation to ensure that differences observed during the study are attributable to the knee.
5. Subjects will ambulate five times over the 18' instrumented gait mat to determine their self-selected walking speed (SSWS) and GVI. Subjects will complete a 2-minute walk test and then be administered the Borg RPE.[5] A heart rate monitor will be worn during the 2 minute walk test in order to calculate physiological cost index (PCI) [6]
6. Subjects will proceed to walk up and down an overground 5-degree ramp for ten trials and then walk up/down a 6-step stair case for ten trials while we measure lower body 3D biomechanics and completion speed.

7. Subjects will walk across a beam while wearing the prosthesis. The beam is very low in height and sits only ~2" inches off the ground.
8. Subjects will walk on a treadmill while wearing the prosthesis while we measure lower body 3D biomechanics.
9. Subjects will then fill out the OPUS HRQOL, LEFS, PEQ, Veteran SF-36, and fall history survey to assess their perception of performance and other health related quality of life factors associated with use of each device. Pilot work with these surveys indicates this will take approximately 30-45 minutes.
10. Subjects will repeat Steps 4-8 with periods of rest provided as necessary until they have completed the full protocol for each of the three MPKs and research grade powered knee.

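### The protocol conflicts with itself on whether the powered knee gets the home acclimation week; if it does not, every powered-knee comparison confounds device with acclimation

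*Combined protocol and SAP*

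**What the plan says.** Study Procedures, Step 4, describes tuning and training in the lab and continues: "Subjects will then proceed to wear the prosthesis for 1 week at home and in the community in order to acclimate to the device". Testing follows on return. No device is exempted. Step 10 repeats Steps 4 to 8 until the subject has "completed the full protocol for each of the three MPKs and research grade powered knee". On this text all four knees get the home week.

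Section 11, Investigator's Qualifications, notes that three of the knees are commercially available and says of them: "These are the devices that will be brought home for 1 week testing protocols with participants". The next sentence turns to the fourth device, the team's own investigational knee, whose testing was approved under a separate but related protocol.

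Step 4 says that acclimation time "is acknowledged to have important implications" for the results. It keeps socket, foot and shoe the same "to ensure that differences observed during the study are attributable to the knee". The Specific Aims apply Aim 1 to "three different commercially available MPKs and one research grade powered knee in 17 individuals with TFA", and Aim 2 uses the same four knees. The Statistical & data analysis plan specifies a repeated measures ANOVA with device as the only within factor and a linear mixed model as fallback. It does not give the number of levels of that factor and has no term for acclimation.

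**The concern.** The two sections cannot both describe the powered knee in their natural sense. If Section 11 describes what happens, the powered knee is tested after in-lab training only and the other three after a week of daily use. A powered-knee difference could then come from the knee, from the missing week, or from both. The attribution that Step 4 is designed to protect would fail for those comparisons, and Aim 3 would carry the mixture into the selection algorithm.

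The questionnaires have the same problem. Step 9 asks about "factors associated with use of each device", which would mean home and community use for three knees and lab use for the fourth.

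**Working it through.** **1. The two texts side by side**

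| Place | Three commercial knees | Powered knee |
|---|---|---|
| Study Procedures, Steps 4 and 10 | Home week | Home week |
| Section 11 | Home week, stated | Set apart; no home week, by implication |

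Other text does not decide between them. The minimum of 5 sessions fits either reading, and the Research Risks section discusses home wear without naming a device.

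**2. Can the two effects be separated?** Take 17 subjects and 4 devices under the Section 11 reading. The design matrix has 17 subject columns and 3 device columns, with rank 20. Adding an indicator for the home week (1 for each commercial knee, 0 for the powered knee) gives 21 columns, but the rank stays 20. The home-week effect therefore cannot be estimated apart from the powered-knee effect. Randomizing order balances period, not acclimation. The mixed model changes the covariance assumptions, not the rank. Of the 4×3/2 = 6 pairwise contrasts, 3 involve the powered knee and are affected; the 3 among commercial knees are not.

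**3. How many levels does the device factor have?** The plan's own power figures give a check. Use the within-factor F test with λ = f²·n·m/(1−ρ), df (m−1) and (n−1)(m−1), and ρ = 0.5 from the plan. Two inputs are assumed because the plan does not give them: α = 0.05 and f = d/2.

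| Outcome | Stated power at about n=9 | m=4, n=9 | m=3, n=9 | m=3, n=10 |
|---|---|---|---|---|
| Borg RPE, d=1 | 90% | 0.922 | 0.856 | 0.899 |
| PEQ, d=0.88 | 80% | 0.834 | 0.752 | 0.807 |

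Four levels reproduce both figures at n=9. Three levels come close with one more subject, so this supports four levels without proving it. The Specific Aims and Step 10 point the same way.

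**4. Illustration of size.** The documents give no acclimation effect, so it is assumed: no true device difference, ρ = 0.5, and a missing home week that shifts the powered knee by a SD. The means are (0, 0, 0, −a), and λ = n·Σ(mean deviation)²/(1−ρ) = n·0.75a²/0.5 = 1.5·n·a². For N=17 and a=0.5, λ = 1.5×17×0.25 = 6.375. The chance that the four-level omnibus test rejects is:

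| α | a | N=17 (target) | N=12 (analysis plan) |
|---|---|---|---|
| 0.05 | 0.25 | 0.151 | 0.116 |
| 0.05 | 0.5 | 0.509 | 0.359 |
| 0.01 | 0.25 | 0.046 | 0.032 |
| 0.01 | 0.5 | 0.265 | 0.153 |

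The 0.01 rows are an assumed stand-in for the plan's multiplicity correction. A simulation with 40,000 runs per cell agrees to within 0.005. A single unadjusted contrast of the powered knee with one commercial knee behaves much the same: 0.16 and 0.49 at N=17, and 0.12 and 0.35 at N=12.

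**The case against.** The strongest reply is that only a wording conflict has been shown. The operative procedures give all four knees the home week, and on that text there is no confounding. The contrary reading rests on a sentence in a section about qualifications, which never says that only those three knees go home. The separate protocol for the investigational knee, not available here, may settle the matter. All of this stands, and it is why the confounding is stated conditionally. It does not remove the need to reconcile the two sections.

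Three smaller points also stand:

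- The acclimation shifts and the 0.01 level are assumptions, so the rejection rates say nothing about the actual effect in this trial. The test of the three take-home knees keeps its nominal level simply because their means were set equal.
- Step 10 literally repeats Steps 4 to 8, which leaves out the Step 9 questionnaires. The questionnaire point relies on Step 9's own reference to each device. The confounding of the performance measures does not depend on it.
- Dropping the powered knee from the factor is not the only remedy. A prespecified test of the three commercial knees inside the four-level model would also serve.

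**Conclusion.** The concern holds. The conflict between Study Procedures and Section 11 is in the current text and nothing in the document resolves it. If the powered knee is not worn at home, confounding is complete for 3 of the 6 pairwise contrasts and enters any omnibus test that includes that knee. No planned analysis can undo it. If it is worn at home, the remedy is a wording correction.

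Under the assumed shifts of 0.25 to 0.5 SD, the false-attribution rate of the omnibus test at α = 0.05 is 15% to 51% at N=17 and 12% to 36% at N=12. Comparisons among the three commercial knees are sound under either reading. This should be fixed before analysis, but it does not undermine the study as a whole.

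**What to change.** Reconcile Steps 4 and 10 with Section 11 on home wear of the powered knee. Which is right is for the investigators. In either case, state the number of levels of the device factor in the analysis plan.

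If the powered knee is not worn at home:

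- Make the three take-home knees the main within factor for Aims 1 and 2.
- Report powered-knee contrasts separately, labelled as following in-lab acclimation only, and do not attribute them to the device alone in Aim 3.
- Use the step counts ("A sensor to collect data about the number of steps participants take will be attached to the prosthesis and/or your shoes") to describe wear of the take-home knees. Adjusting powered-knee contrasts for them would be extrapolation, so it belongs only in a labelled sensitivity analysis.

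The cost is wording plus, under one reading, some best-case power. Take the PEQ effect d=0.88 as the largest difference between knees, with α = 0.05 and ρ = 0.5. Then f is at most 0.5d = 0.44 with four levels and 0.471d = 0.415 with three.

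| Test (best pattern of means) | N=17 | N=12 | n=9 |
|---|---|---|---|
| Four levels | 0.992 | 0.941 | 0.834 |
| Three levels, separate model | 0.956 | 0.845 | 0.698 |
| Three commercial knees tested within the four-level model | 0.962 | 0.862 | 0.728 |

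The third row keeps the powered knee in the model and pools the error, with 3(n−1) error degrees of freedom, so it recovers a little power. At n=9 both three-knee options fall below the plan's stated 80%; at N=12 and N=17 neither does. In the least favourable pattern, with the other knees midway between the extremes, three levels do better than four (0.882 against 0.845 at N=17), so the loss is not certain.

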## **12. Funding Sources**

This work is funded by the Department of Defense through the Congressional Directed Medical Research Program (CDMRP). The grant title is Personalizing MPK Prescription for Individuals With Transfemoral Amputation. None of the researchers involved in this study have conflict of interest.

